## 5.12. Exploratory Objectives Analyses

As mentioned in Section 5.2, exploratory objectives will be analyzed for ARS in Group A+B unless otherwise specified.

The plan of analysis for the exploratory pharmacogenetic objective is in Section 5.15 of this document.

### 5.12.1. Patient Reported Outcome

The TRIM-D and TRIM-DD will be administered at Visit 4 (Week 0, prior to randomization), at Visit 13 (Week 14) and at Visit 17 (Week 26) or ET if subjects do not complete the full 26 weeks of the study.

If a respondent answers at least half of the items in a multi-item domain (or half plus one in the case of domains with an odd number of items) then a domain score should be calculated. The average score (across completed items in the same domain) for that respondent will be used to estimate any missing item in that domain. For example, if a respondent leaves 1 item in the 5-item Diabetes Management domain blank, substitute the respondent's average score (across the 4 answered Diabetes Management items) for the missing score for that item.

For both TRIM-D and TRIM-DD, the domain score and overall score will be transformed to a 0-100 scales by  $\text{Domain} = (\text{raw score} - \text{lowest possible raw score}) / \text{possible raw score range} * 100$ . The transformed score will be used for the analysis purpose.

#### 5.12.1.1. TRIM-D

The TRIM-D consists of 28 items which are measured on a 5-point scale, where a higher score indicates a better health state. In addition to an overall score, the TRIM-D items make up the 5 domains of impact: treatment burden (6 items), daily life (5 items), diabetes management (5 items), compliance (4 items) (see Section 5.7), and psychological health (8 items). The domains of daily life, compliance, and psychological health need to be reverse coded for scoring.

Summaries of domain and overall transformed scores will include sample size, mean, SD, median, minimum, and maximum at each assessment at each visit for each treatment group and for the ARS population. The actual value and change from baseline (Visit 4) will be summarized for the overall analysis population. The actual value and change from baseline in domain transformed scores and total transformed scores of TRIM-D will be analyzed using an MMRM approach. The MMRM model will include the following fixed effects: treatment (U-500R CSII, U-500R MDI), weeks on treatment, the interaction between treatment and weeks, and the stratification factors (U-500R at entry versus other insulins, entry HbA1c  $\geq 8.5\%$  or  $< 8.5\%$  and nonusers versus users of GLP-1 receptor agonists or SGLT2 inhibitors). The model will also include the corresponding baseline measures as a covariate. The covariance matrix will be chosen in the same order as the primary analysis.

The proportion of subjects who have TRIM-D compliance transformed score  $\geq 80$  at endpoint or ET will be analyzed using logistic regression with the following fixed effects: treatment (U-500R CSII, U-500R MDI) and the stratification factors (U-500R at entry versus other insulins, entry HbA1c  $\geq 8.5\%$  or  $< 8.5\%$ , and nonusers versus users of GLP-1 receptor agonists or SGLT2 inhibitors).

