## 5.7. Treatment Compliance

The analyses described in this section will be done for both Group A and Group A+B. Compliance issues, as stated in study protocol Section 9.12, will be listed and summarized as protocol deviations and details can be found in this SAP (Section 5.8). Summaries of actual value and change from baseline (Visit 4) of TRIM-D compliance transformed score will include sample size, mean, SD, median, minimum, and maximum at each assessment at each visit for each treatment group and for the ARS population. The actual value and change from baseline in compliance scores will be analyzed using an MMRM approach.

For Group A, the MMRM model will include the following fixed effects: treatment (U-500R CSII, U-500R MDI), weeks on treatment, the interaction between treatment and weeks, and the stratification factors (U-500R at entry versus other insulins, entry HbA1c  $\geq 8.5\%$  or  $< 8.5\%$ ). The model will also include the corresponding baseline of the response variable.

For Group A+B, the same MMRM model in Group A above will be used with the addition of the stratification factor (nonusers versus users of GLP-1 receptor agonists or SGLT2 inhibitors).

The proportion of subjects who have TRIM-D compliance score  $\geq 80$  at endpoint or ET will be analyzed using logistic regression including the similar fixed effects used in primary analysis.

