- proportions of subjects achieving HbA1c targets/values ( $\leq 6.5\%$ ,  $< 7.0\%$ ,  $< 7.5\%$ , and  $< 8.0\%$ )
- proportions of subjects achieving HbA1c targets/values ( $\leq 6.5\%$ ,  $< 7.0\%$ ,  $< 7.5\%$ , and  $< 8.0\%$ ) without documented symptomatic hypoglycemia (SMBG  $< 50$  mg/dL)

The logistic regression model will include similar fixed effects as in the above ANCOVA and MMRM models. The proportion of subjects achieving HbA1c targets with no documented symptomatic hypoglycemia (from baseline to the corresponding visit) will be analyzed using similar logistic regression models including the baseline documented symptomatic hypoglycemia event rate as a covariate.

Analyses to assess the following 2 secondary objectives are presented in Section 5.13 since those are considered safety measures:

- rate and incidence of hypoglycemia (documented [documented symptomatic, asymptomatic, and unspecified], severe, and nocturnal)
- change in body weight between treatment groups and as a function of change in HbA1c

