### 5.11. Exploratory Efficacy Analysis

As mentioned in Section 5.2, exploratory objectives will be analyzed for Group A+B. Summary statistics for both actual values and CFBL values will be reported for each treatment by visit for the following parameters related to 7-point SMBG:

- within-day glucose variability measured by the SD of 7-point SMBG
- between-day glucose variability measured by the SD of the SMBG during the 2-nonconsecutive-day measurement within the same scheduled visit
- within-day and between-day glucose coefficient of variation (CV) of 7-point SMBG (Clarke and Kovatchev 2009)
- average daily risk range (ADRR) defined by (Kovatchev et al. 2006)

- mean of daily differences (MODD) calculated as the average of the difference between values on different days within the same scheduled visit but at the same time

Each of the parameters above will be analyzed using an MMRM model which includes the following fixed effects: treatment (U-500R CSII, U-500R MDI), weeks on treatment, the interaction between treatment and weeks, and the stratification factors (U-500R at entry versus other insulins, entry HbA1c  $\geq 8.5\%$  or  $< 8.5\%$ , and nonusers versus users of GLP-1 receptor agonists or SGLT2 inhibitors). The model will also include the corresponding baseline of the response variable. An ANCOVA will also be used to compare treatment arms at endpoint using the LOCF method. The ANCOVA model will include the same fixed effects in the MMRM model but without the terms involving weeks

The postprandial contribution to total hyperglycemia will be further explored (Riddle et al. 2011). The daily blood glucose (BG) response to meals will be estimated by calculating the incremental AUC of daytime BG from the overall glucose profile. Four areas were calculated geometrically from the seven-point curve as follows:

- 1) normal glycemic exposure ( $AUC_N$ ):  $100 \text{ mg/dL} \times 24 \text{ h} = 2,400 \text{ mg/dL per hour of exposure}$
- 2) basal hyperglycemia (BHG) ( $AUC_B$ ): the area between  $100 \text{ mg/dL}$  and a line projected rightward for 24 hours from the fasting (before breakfast) glucose value in the profile (the area is taken to represent the daily abnormal glycemic exposure resulting from BHG)

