- 3) postprandial hyperglycemia (PPHG) ( $AUC_P$ ): the area above the line projected rightward from the fasting sample before breakfast and below the line connecting the 6 remaining points, minus any area below the line projected from the basal value, if applicable (this area is considered a reflection of the postprandial glycemic responses to breakfast, lunch, and dinner)
- 4) total glucose ( $AUC_G$ ): the total area under the glucose curve is the sum of the other 3 areas [ $AUC_G = AUC_N + AUC_B + AUC_P$ ]. As a result, the relative contributions of postprandial and fasting BG to the total BG increment were calculated, respectively, by using the following equations: [ $AUC_P / (AUC_B + AUC_P)$ ] x 100% for the postprandial contribution and [ $AUC_B / (AUC_B + AUC_P)$ ] x 100% for the basal contribution. Negative values were set to zero.

Analyses include Mean (SD) of and Pearson correlation (p-value) between HbA1c CFBL at Week 26 (LOCF) and each of CFBL of:  $AUC_B$ ,  $AUC_P$ ,  $AUC_G$ , BHG contribution and PPHG contribution at Week 26 (LOCF). The  $AUC_B$  and  $AUC_P$  will be analyzed separately by fitting ANCOVA model with baseline corresponding parameter as a covariate, treatment as fixed effect to compare the treatment effect.

Total hyperglycemia (%) separated by BHG and PPHG will be plotted for each treatment in bar chart format with x-axis for different HbA1c category ( $< 6.5\%$ ,  $6.5\%$  to  $< 7\%$ ,  $7\%$  to  $< 7.5\%$ ,  $7.5\%$  to  $< 8\%$ ,  $\geq 8\%$ , and overall).

Proportions of subjects with HbA1c  $\geq 9\%$  or  $< 9\%$  at Week 26 will be reported and will be analyzed using the same logistic regression model used in the analysis of the proportions of subjects achieving different HbA1c targets in Section 5.10.

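### Two exploratory arm comparisons omit prognostic terms the trial already holds: the baseline score in the TRIM-D compliance responder model, and the randomization strata in the AUC ANCOVA

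*SAP*

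**What the plan says.** **Responder model.** SAP 5.12.1.1 takes the proportion of subjects with a transformed TRIM-D compliance score of 80 or more at endpoint or early termination. It "will be analyzed using logistic regression with the following fixed effects: treatment (U-500R CSII, U-500R MDI) and the stratification factors", and then names three factors: U-500R at entry, entry HbA1c split at 8.5%, and GLP-1/SGLT2 use. No baseline score is listed. For the continuous TRIM-D scores, the paragraph above does adjust: "The model will also include the corresponding baseline measures as a covariate". SAP 5.12.1 places the first TRIM-D assessment at Visit 4, before randomization.

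SAP 5.7 plans the same responder analysis for Group A and for Group A+B, but says only that it "will be analyzed using logistic regression including the similar fixed effects used in primary analysis". The primary ANCOVA in SAP 5.9 has treatment, one stratification factor (U-500R at entry) and baseline HbA1c as covariate. GLP-1/SGLT2 use is added for Group A+B.

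**AUC model.** SAP 5.11 analyzes AUC_B and AUC_P "separately by fitting ANCOVA model with baseline corresponding parameter as a covariate, treatment as fixed effect to compare the treatment effect". For the glucose variability measures in the same section, the wording is "Each of the parameters above will be analyzed using an MMRM model which includes the following fixed effects", and that list carries all three strata, with baseline as well. Protocol 9.6 confirms that randomization was stratified by these three factors.

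**Practice elsewhere.** For HbA1c targets reached without hypoglycemia, SAP 5.10 plans "similar logistic regression models including the baseline documented symptomatic hypoglycemia event rate as a covariate". An endpoint-specific baseline covariate in a responder model is therefore already part of the plan's approach.

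**The concern.** A baseline measurement of the same scale is normally a strong predictor of the endpoint. Leaving it out of a logistic model discards information already paid for. The two descriptions of the responder model also cannot both be programmed as written, so someone must choose between them, possibly after seeing results.

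In the AUC model, the randomization balances the arms on three factors, but the analysis leaves the variance due to those factors in the residual. The reported standard error is then larger than the design warrants. What is at stake is power and a clean specification in two exploratory comparisons, not the validity of either test.

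**Working it through.** **1. The plan's own powered figure.** SAP 5.1 gives a margin of 0.4, SD 1.1, two-sided alpha 0.05, 80% power and 240 Group A completers. n per arm = 2 × (1.96 + 0.8416)² × 1.1² / 0.4² = 2 × 7.849 × 1.21 / 0.16 = 118.7, so 119 per arm or 238 in total, against 240 stated. At 120 per arm the power is 0.804, and 240 / 0.75 = 320 randomized. The figure reproduces. The documents state no power for the two exploratory comparisons.

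**2. Sample for the exploratory comparisons.** They use Group A+B (SAP 5.11 and 5.12). Expected completers are 240 + 48 = 288 to 240 + 72 = 312, or 144 to 156 per arm. The simulations use 312, with permuted blocks of four within eight strata. GLP-1/SGLT2 users are 23% (72 / 312); the other two stratum shares, 30% and 50%, are assumed. Scores from early termination visits could make the sample somewhat larger.

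**3. The two responder models side by side.**

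| Term (besides treatment) | SAP 5.12.1.1 (A+B) | SAP 5.7, read through 5.9 |
|---|---|---|
| U-500R at entry | yes | yes |
| Entry HbA1c stratum | yes | no |
| GLP-1/SGLT2 use | yes | A+B only |
| Baseline HbA1c | no | yes, if covariates carry over |
| Visit 4 compliance score | no | not named |

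**4. Power of the responder model.** Assumed: about 50% MDI responders, a treatment shift of 0.33 SD on a latent normal score, strata with no effect on the outcome, and baseline-to-endpoint correlation r. There were 2,000 runs per setting.

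| r | log OR without → with baseline score | SE without → with | Power without → with |
|---|---|---|---|
| 0.3 | 0.537 → 0.571 | 0.233 → 0.241 | 0.638 → 0.663 |
| 0.5 | 0.533 → 0.645 | 0.233 → 0.257 | 0.628 → 0.705 |
| 0.7 | 0.533 → 0.804 | 0.232 → 0.291 | 0.629 → 0.790 |

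The ratio of estimate to SE explains the gain. At r = 0.5 it is 0.533 / 0.233 = 2.29 without the score and 0.645 / 0.257 = 2.51 with it. The SE rises, but the log odds ratio rises more. Under no treatment effect, the planned model's average SE is 0.228 against a sampling SD of 0.224 to 0.234, and its type I error is 0.044 to 0.051. The planned model is valid.

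**5. Standard error of the AUC ANCOVA.** If the strata explain a fraction R² of the variance left after baseline AUC, the SE without strata is larger by the factor 1 / √(1 − R²):
- R² = 0.02: 1 / √0.98 = 1.010
- R² = 0.05: 1 / √0.95 = 1.026
- R² = 0.10: 1 / √0.90 = 1.054

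Simulation (5,000 runs, baseline correlation about 0.5, effect set for about 80% power) gives the same factors. Power moves from 0.796 to 0.801, 0.810 to 0.823, and 0.811 to 0.840. At R² = 0.10 the model SE without strata is 0.098, against a true sampling SD of about 0.091 to 0.094, so it is too wide. Type I error falls to 0.045 at R² = 0.05 and 0.037 at R² = 0.10. As a check at 0.10: 1.96 × 1.054 = 2.066, which has a two-sided tail of 0.039. At R² = 0 nothing changes.

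**The case against.** The strongest reply is that little depends on these models. Both comparisons are exploratory and outside the alpha-controlled hypotheses H1 to H10. The planned responder test holds its level, and the AUC test errs on the safe side. Adding the baseline score also changes the target: the odds ratio becomes conditional on baseline, while the stated interest is the proportion reaching 80. Subjects without a computable baseline domain score would drop out. All of this stands. It limits the point to a small improvement and must be dealt with in the fix.

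It is also fair that the sizes rest on assumptions. The documents give no responder rate, no correlation, no AUC SD and no share of variance due to strata. At r = 0.3 the responder gain is only two to three points.

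Three stronger readings are tempting, and the documents do not support them:
- A reader might infer that the responder model's standard errors are too wide. They are not. Its SE matches its sampling SD, and adding the score makes the SE larger. The loss comes through the attenuated odds ratio.
- A reader might take Protocol 12.2.6, which limits compliance data for analysis to the questionnaires, to mean that the responder analysis is the only quantitative comparison of compliance. SAP 5.7 also plans a baseline-adjusted MMRM of the continuous compliance score, so the responder analysis is supplementary.
- A reader might say that SAP 5.7 definitely leaves out the baseline score. Its wording is too loose to establish that. What is established is that it does not match 5.12.1.1.

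**Conclusion.** The point holds as a low-priority improvement. The responder model in SAP 5.12.1.1 omits a collected pre-randomization predictor and is specified in two incompatible ways. The cost is about 2 to 16 percentage points of power for assumed correlations of 0.3 to 0.7, with 312 completers. The AUC ANCOVA ignores all three factors used in randomization. Its standard error is conservative by about 1% to 5% if the strata explain 2% to 10% of residual variance, and not at all if they explain nothing. The direction of each effect follows from the models; the sizes depend on the assumptions stated. There is no bias in the randomized comparison and no inflated type I error, and no primary or key secondary conclusion is affected.

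**What to change.** Use one logistic model for the compliance score of 80 or more, written out in full in SAP 5.12.1.1 and cited from 5.7. Its terms are treatment, U-500R at entry, entry HbA1c stratum, the Visit 4 transformed compliance score, and GLP-1/SGLT2 use for Group A+B only. State that the odds ratio is conditional on baseline, and show the observed proportions by arm beside it. State in advance how a missing baseline score is handled. Under the half-of-items rule in SAP 5.12.1, a subject with fewer than two of the four compliance items answered has no score.

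Add U-500R at entry, entry HbA1c stratum and GLP-1/SGLT2 use to the AUC_B and AUC_P ANCOVA.

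The cost is a few lines of SAP text and two model statements. Every variable is already collected. The price is the conditional interpretation and the possible loss of subjects without a baseline score, a requirement the planned baseline-adjusted MMRM already shares. The change should be made before the study team sees treatment assignments. If that point has passed, report the revised models as additional analyses.

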#### **5.12.1.2. TRIM-DD**

The TRIM-DD consists of 8 items which are measured on a 5-point scale, where a higher score indicates a better health state. In addition to an overall score, the TRIM-DD items make up the 2 domains of impact: device function (5 items) and bother of device (3 items). The bother of device domain need to be reverse coded for scoring.

Summaries of domain and overall transformed scores will include sample size, mean, SD, median, minimum, and maximum at each assessment at each visit for each treatment group and for the ARS population. The actual value and change from baseline (Visit 4) in domain and total transformed scores of TRIM-DD will be summarized and analyzed using an MMRM approach. The MMRM model will include the following fixed effects: treatment (U-500R CSII, U-500R MDI), weeks on treatment, the interaction between treatment and weeks, and the stratification factors (U-500R at entry versus other insulins, entry HbA1c  $\geq 8.5\%$  or  $< 8.5\%$ , and nonusers versus users of GLP-1 receptor agonists or SGLT2 inhibitors). The model will also include the corresponding baseline values as a covariate. The covariance matrix will be chosen in the same order as the primary analysis.

#### **5.12.1.3. OmniPod U-500 System Exit Questionnaire**

The percentage of subjects giving each answer to each question on the OmniPod U-500 System Exit Questionnaire will be summarized. The percentage will also be broken down by gender, and age ranges (18 to  $< 25$ , 25 to  $< 35$ , 35 to  $< 45$ , 45 to  $< 55$ , 55 to  $< 65$ , 65 to  $< 75$ , and  $\geq 75$  years).

### ***5.12.2. Functionality and Safe Use of the OmniPod U-500 System***

The functionality and safe use of the OmniPod U-500 system will be evaluated by an assessment of device complaint data, subject reported hazard alarms, and clinically relevant hyperglycemia possibly related to site occlusion. A listing of reported hazard alarms associated with routine and non-routine site changes as well as a listing of non-routine site changes with no alarms associated with hyperglycemia will be provided.

### **5.12.3. Subgroup Analysis**

For the primary objective (Section 4.1 of the SAP), the following subgroup analyses will be performed for Group A if at least 20 subjects in each treatment group are in each of the subgroups: baseline TDD  $> 2$  and  $\leq 2$  units/kg, baseline TDD  $> 400$  and  $\leq 400$  units, TDD  $> 200$  units at baseline that fall below TDD 200 units during the study and TDD  $> 200$  units at baseline that stay 200 units or above during the study, and geriatric subjects (age  $< 65$  and  $\geq 65$  years; and age  $< 75$  and  $\geq 75$  years). Within each strata of the specific subgroup, analysis will be performed using the similar model for the primary efficacy analysis using MMRM. To assess treatment by subgroup interaction, analysis will be conducted by adding subgroup as a main

effect and interaction term between treatment and subgroup, the 3-way interaction of the primary treatment arms, visit, and the subgroup variable will also be added for the MMRM analysis model. The interaction effects will be tested at significance level of 0.10.

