It is estimated that 10% to 18% of patients treated with U-500R are on concomitant noninsulin injectable therapy, including glucagon-like peptide-1 (GLP-1) receptor agonist therapy (Eby et al. 2013, 2014 and Data on File). Although the percentage of U-500R used in combination with sodium-glucose co-transporter 2 (SGLT2) inhibitors is unknown, combination of SGLT2 inhibitors with U-100 insulin has risen by 4-fold to 1.4% (July 2013 to April 2014 [IMS Data on File]). GLP-1 receptor agonists and SGLT2 inhibitors have been used in insulin-sparing and weight attenuating strategies and have shown clinical utility in combination with U-500R or U-100 insulin (Lane et al. 2011; Rosenstock et al. 2014). Two study population groups (Groups A and B) will be stratified by nonuse or use of these therapies. Subjects in each group will be randomly assigned equally between treatment arms. Study population Group A will include patients who are not using GLP-1 receptor agonists or SGLT2 inhibitors. The study population Group B will include patients who are using GLP-1 receptor agonists or SGLT2 inhibitors. Group A will be the primary analysis population. Combined Groups A and B will be included in the key and other secondary objectives. The use of GLP-1 receptor agonists or SGLT2 inhibitors is also intended for exploratory analyses.

Appropriate testing supporting use of the U-500R in the OmniPod U-500 Insulin Management System in clinical trials has been completed. More detailed information about the known and expected benefits and risks of U-500R may be found in the U-500R package insert. More

detailed information regarding the use of the OmniPod U-500 system may be found in the OmniPod U-500 Insulin Management System User Guide.

6. Objectives

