6.2. Secondary Objectives

6.2.1. Key Secondary Objectives

The following 4 key (alternative hypotheses [H#]) secondary objectives at Week 26 are to demonstrate for the main study population (Group A [without use of GLP-1 receptor agonists or SGLT2 inhibitors, Section 7.1]) that:

H2: CSII is superior to MDI in change in fasting plasma glucose (FPG).

H3: CSII is superior to MDI in proportions of subjects achieving HbA1c targets/values $<7.0\%$.

H4: CSII is superior to MDI in change in HbA1c.

H5: CSII is superior to MDI in proportions of subjects achieving HbA1c targets/values $<7.5\%$.

The following 5 key (alternative hypotheses [H#]) secondary objectives are to demonstrate the objectives at Week 26 for the total study population (Group A [without use of GLP-1 receptor agonists or SGLT2 inhibitors] and Group B [those who use GLP-1 receptor agonists or SGLT2 inhibitors use, Section 7.1]) that:

H6: CSII is noninferior to MDI in change in HbA1c using NIM of 0.4%.

H7: CSII is superior to MDI in change in FPG.

H8: CSII is superior to MDI in proportions of subjects achieving HbA1c targets/values $<7.0\%$.

H9: CSII is superior to MDI in change in HbA1c.

H10: CSII is superior to MDI in proportions of subjects achieving HbA1c targets/values $<7.5\%$.

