### 3. Revision History

This is the second version of the Statistical Analysis Plan (SAP) for Study B5K-MC-IBHD (IBHD). This version is based on protocol amendment B5K-MC-IBHD(a) approved on 07 December 2016. The first version of the SAP for Study IBHD was approved on 17 September 2015 based on original protocol B5K-MC-IBHD.

Some changes in the SAP were made on request from the US Food and Drug Administration (FDA).

The overall changes and rationale for the changes made to this SAP are as follows:

- Elaborated on the safety and efficacy analyses and handling of missing data in “Statistical and Analytical Plans” (Sections 5.2, 5.9, 5.10). The SAP now provides for multiple analysis methods of the primary and key secondary objectives to account for missing data. Based on US FDA request, the Intent-to-Treat (ITT) estimand that accounts for all observed data, including those for subjects who have stopped study drug but continued in the study, will be used for the primary analysis of the All Randomized Set (ARS) and will be analyzed using copy reference multiple imputation analyses with analysis of covariance (ANCOVA). For publications and regulatory purposes in other regions, the efficacy estimand that includes only data observed while subjects were receiving study drug (excludes data after subjects discontinued study drug but remained in study) will be used for the primary analysis using mixed model repeated measures (MMRM). Two sets of similar analysis approaches (MMRM and multiple imputation based ANCOVA) as those for the primary objective will be used for key secondary endpoints.
- The Disposition section (Section 5.4) was edited to remove non-essential summary analyses.
- Edited “Concomitant Therapy” (Section 5.6) to remove analyses typically not included in parallel studies.
- Non-essential listings were removed from the SAP.
- The analyses for the different groups (Group A and Group A+B) were clarified. Analyses for primary and key secondary objectives will be done for Group A and Group A+B. Analyses not for primary and key secondary objectives (including exploratory objectives and safety evaluations not used to assess secondary objectives) will be done for Group A+B only. Subgroup analyses will be done for the primary objective and for Group A only.

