#### **4.3. Exploratory Objectives**

Exploratory objectives of the study are the following and will be assessed for the total study population (Group A+B):

- The change in patient reported outcomes including Treatment-Related Impact Measure for Diabetes (TRIM-D) and TRIM-D for Diabetes Device (TRIM-DD) surveys from baseline to 26-week value.
- Assess subject-reported OmniPod pump experience via OmniPod U-500 System Exit Questionnaire.
- Assess proportion of subjects with an HbA1c  $\geq 9\%$  and  $< 9\%$  at the 26-week value.
- Postprandial contributions to total glycemic burden at baseline to 26-week values using area under the curve (AUC) analysis of 7-point SMBG profiles.
- Glycemic variability using 7-point SMBG profiles (including within day and day-to-day standard deviation [SD], coefficient of variation, average daily risk range, and mean of daily differences).
- Examine the relationship between gene variants including, but not limited to, insulin receptor, insulin like growth factor-1, melatonin receptor 1B1, adiponectin, transcription factor 7-like 2, phosphoinositide-3-kinase, regulatory subunit 1 and B-cell CLL/lymphoma 11A on clinical outcomes.

- Evaluate subgroups of baseline TDD >2 and ≤2 units/kg, TDD >200 units at baseline that fall below TDD 200 units during the study, baseline TDD >400 and ≤400 units, users of GLP-1 receptor agonists or SGLT2 inhibitors, and geriatric subjects (age ≥65 years and ≥75 years) on each of the primary and secondary objectives.
- Functionality and safe use of the OmniPod U-500 system.

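### GLP-1 agonist or SGLT2 inhibitor users are a named subgroup objective, but subgroup analyses are confined to Group A, which has no users, so the objective has no planned analysis

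*SAP*

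**What the plan says.** **Objective.** Protocol 6.3 and SAP 4.3 both list subgroups to be examined on the primary and secondary objectives. The list includes "users of GLP-1 receptor agonists or SGLT2 inhibitors, and geriatric subjects", alongside dose subgroups. SAP 4.3 adds that the exploratory objectives "will be assessed for the total study population (Group A+B", meaning users and nonusers together.

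**Analysis.** SAP 5.12.3 covers the primary objective only: "the following subgroup analyses will be performed for Group A", provided that 20 or more subjects per arm fall in each subgroup. Its list holds the dose and age subgroups but not user status. The SAP revision history states the restriction outright: "Subgroup analyses will be done for the primary objective and for Group A only".

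**Who is in Group A.** Protocol section 5: "Study population Group A will include patients who are not using GLP-1 receptor agonists or SGLT2 inhibitors".

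**Pooled claims.** H6 to H10 are alpha-controlled claims for Group A+B, starting with noninferiority on HbA1c at a margin of 0.4%. SAP 5.9 and 5.10 add user status to the A+B models as a fixed effect, with no treatment-by-user term. SAP 5.2 allows Group B-only analyses at the sponsor's discretion, with safety as the example and no endpoint or model named.

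**The concern.** Followed as written, the SAP leaves a stated objective without an analysis. A subgroup of users cannot be formed inside a population defined by non-use.

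The gap matters because the trial also makes formal claims for the combined population. A main effect for user status lets the mean HbA1c change differ between users and nonusers. It does not let the CSII-minus-MDI difference vary, and it cannot show whether that difference does vary. Group B is a minority of the pooled completers, so a pooled noninferiority result could stand while users do worse on CSII by more than the margin, with no planned estimate for users to set beside it.

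**Working it through.** **Inputs.** From SAP 5.1 (and protocol 12.1): margin 0.4%, SD 1.1%, two-sided alpha 0.05, 1:1 allocation, 240 Group A completers (120 per arm), 48 to 72 Group B completers (24 to 36 per arm), 25% dropout. From SAP 5.12.3: interaction level 0.10 and at least 20 subjects per arm. Assumptions: SD 1.1% also holds in Group B, and the pooled estimate weights the groups by size.

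**The plan's own figure.** With a true difference of 0, n per arm = 2 × (1.96 + 0.842)² × 1.1² / 0.4² = 119, or 238 in total against 240 stated. Power at 120 per arm is 80.4% against 80% stated. 240/0.75 = 320, 48/0.75 = 64 and 72/0.75 = 96, all as stated. No stated figure is wrong.

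**How H6 is reached.** The worked example in protocol 12.2.2 gives most of the weights.
- H1 sends 0.01 to H2 and 0.04 to H3, which is all of its 0.05.
- H3 sends 99% to H2 and 1% to H4, which is all of its alpha.
- Once H3 is rejected, H2 sends 100% to H4.
- When H4 then fails at 0.05, the procedure stops.

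So H1 to H3 pass nothing directly to H5 to H10. Alpha gets there only through H4, superiority on HbA1c in Group A. The weights leaving H4 are in a figure that is not shown.

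**An example consistent with that order.** Take observed differences (CSII minus MDI) of -0.30 in A and +0.60 in B, with 240 and 72 completers.
- Group A: SE = 1.1 × √(4/240) = 0.142. Upper 95% limit = -0.30 + 1.96 × 0.142 = -0.02. H4 is met at 0.05, the level it holds once H2 and H3 have both been rejected.
- Pooled estimate = (240 × -0.30 + 72 × 0.60)/312 = -0.09.
- Pooled SE = 1.1 × √(4/312) = 0.125. Upper limit = -0.092 + 0.244 = 0.15, well under 0.4, so H6 is met.
- With 48 in Group B: pooled estimate = (240 × -0.30 + 48 × 0.60)/288 = -0.15, SE 0.130, upper limit 0.10. H6 is again met.

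The Group B estimate of 0.60 lies beyond the margin in both cases.

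**What the missing analysis would show.**

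| | B: 24 per arm | B: 36 per arm |
|---|---|---|
| Share of A+B completers | 16.7% | 23.1% |
| SE of Group B difference, 1.1 × √(2/n) | 0.318 | 0.259 |
| 95% half-width | 0.62 | 0.51 |
| SE of interaction, 1.1 × √(2/120 + 2/n) | 0.348 | 0.296 |
| Power at 0.10, interaction of 0.4 | 31% | 39% |
| Power at 0.10, interaction of 0.8 | 74% | 86% |
| Interaction detectable with 80% power | 0.86 | 0.74 |

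In the example the interaction is 0.60 - (-0.30) = 0.90, giving z = 0.90/0.348 = 2.6 or 0.90/0.296 = 3.0. Both exceed the 1.645 needed at the 0.10 level. Planned completers (24 to 36 per arm) also satisfy the 20-per-arm rule.

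**The case against.** The Group A restriction is deliberate. The revision history states it, and SAP 5.12 uses Group A+B for exploratory objectives only where nothing else is specified. That settles the population for the dose and age subgroups. It does not settle user status, which SAP 4.3 still lists and which cannot be studied in Group A. Trimming 4.3 would remove the contradiction, but would leave the pooled claims without a planned look by user status.

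A reader might infer that a neutral Group A could carry H6 while Group B is clearly worse. The documents do not support that. With a true difference of 0 in A, H4 succeeds in favour of CSII at most about 2.5% of the time, so H6 would rarely be tested. Even ignoring the order, true differences of 0 in A and 0.6 in B (72 completers) give a pooled mean of 0.138 against a pass limit of 0.4 - 0.244 = 0.156. H6 would then pass only about 56% of the time.

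A reader might also infer that nothing in the plan would reveal a difference. That is too strong. Results are reported for A and for A+B, so a rough Group B value can be backed out: in the example, (-0.092 + 0.231)/0.231 = 0.60. Group B-only analyses are also permitted. Neither is a planned Group B estimate, interval or interaction test.

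The low-power objection stands. The half-width exceeds the margin, and Group B may close below its minimum enrolment, so the result can only be descriptive.

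**Conclusion.** The point holds as an inconsistency between objective and analysis: a subgroup named in both documents has no planned analysis, and the population set for subgroup work excludes it. The consequence is limited to the A+B claims; H1 to H5 in Group A are unaffected.

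The relevant case is benefit in A masking harm in B. The example shows what the plan permits and does not forecast a result. It rests on SD 1.1% in both groups, size-weighted pooling, and the SAP using the same graph as the protocol's worked example; the SAP drops the example but lists no change to multiplicity. The alpha reaching H6 is not visible, but the conclusion is not sensitive to it: z against the margin is (0.4 + 0.092)/0.125 = 3.9.

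This should be corrected, but it does not threaten the primary result.

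**What to change.** Add user versus nonuser to SAP 5.12.3, run in Group A+B with the subgroup MMRM already described there (treatment-by-user and treatment-by-visit-by-user terms). Report the Week 26 HbA1c difference and 95% CI by user status beside H6. Exempt this subgroup from the 20-per-arm rule so that the estimate appears even if Group B closes early. Label it descriptive and give the expected precision.

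Also align scope: SAP 4.3 promises subgroup work on the secondary as well as the primary objectives, while 5.12.3 covers only the primary. Either extend 5.12.3 or narrow 4.3 and record the departure from protocol 6.3.

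The cost is one extra model and table. User status is already a stratification factor, so no new data are needed. The downside is a low-power result, in which a null interaction must not be read as evidence of consistency.
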